## **SAFETY AND TOLERANCE**

- Incidence and severity of AEs from routine monitoring
- Incidence of abnormalities and changes from baseline in clinical laboratory parameters from testing of blood and urine
- Incidence of adverse changes from baseline vital sign values
- Incidence of adverse changes from baseline physical examinations
- Safety parameters will also be summarized by genetic subset to identify possible trends

## **SAFETY EVALUATION**

All patients who have received at least one dose, or any part of one dose, of study drug and have a subsequent safety evaluation will be included in the safety analyses. All adverse events reported during the study will be listed, documenting course, severity, relationship to study drug, and outcome. Adverse events will be coded to MedDRA terms.

Adverse events will be summarized, giving the number of patients who experienced an adverse event, the maximum severity, relationship to study drug and body system. Laboratory parameters, vital signs, and physical exam results will be listed and summarized with the statistics of number of patients, mean, standard deviation, median and range or frequencies and percentages, as appropriate, from baseline to each subsequent visit.

## **ASSESSMENT OF SAFETY**

Periodic safety review will be performed during the on-treatment period by a data and safety monitoring board (DSMB) to include surveillance of laboratory testing and on-treatment safety events so as to advise the study management team regarding potential changes in patients monitoring or treatment plans during the remaining treatment period.

## 2 LIST OF ABBREVIATIONS

ABCA1	ATP Binding Cassette transporter A1
ACS	Acute Coronary Syndrome
ADR	Adverse Drug Reaction
AE	Adverse Event
ANCOVA	Analysis of Covariance
ApoA-1	Apolipoprotein A-1
BMI	Body Mass Index
BP	Blood Pressure
BUN	Blood Urea Nitrogen
CABG	Coronary Artery Bypass Graft
CAD	Coronary Arterial Disease
CE	Cholesterol Ester
CER-001	Experimental compound under study
CHD	Coronary Heart Disease
CHO	Chinese Hamster Ovary
CK	Creatine Kinase
CRF	Case Report Form
CRO	Clinical Research Organization
CSR	Clinical Study Report
CVD	Cardiovascular Disease
DSMB	Data Safety Monitoring Board
ECG	Electrocardiogram
eCRF	Electronic case report form
ESF	Eligibility Screening Form
FDA	Food and Drug Administration
 FDG-PET/CT	 F-Fluorodeoxyglucose-Positron Emission Tomography/Computerized Tomography
FH	Familial Hypercholesterolemia
FPHA	Familial Primary Hypoalphalipoproteinemia
HbA1c	glycated Hemoglobin A1C
HDL	High density lipoprotein
HDL/LDL RATIO	High density lipoprotein/low density lipoprotein ratio
HDL-C	High density lipoprotein cholesterol
HEENT	Head, Ears, Eyes, Nose, Throat
HPLC	High-Pressure Liquid Chromatography
HR	Heart Rate
hsCRP	high sensitivity C-reactive protein
ICH	International Conference on Harmonization
IL-6	Interleukin 6
IMP	Investigational Medicinal Product
IRB/IEC	Institutional Review Board/Independent Ethics Committee
ITT	Intent-to-Treat
IUD	IntraUterin Device
IVUS	IntraVascular UltraSound
IWRS	Interactive Web Response System
LCAT	Lecithin Cholesterol AcylTransferase
LDH	Lactate dehydrogenase
LDL	Low density lipoprotein
LDL-C	Low density lipoprotein cholesterol

MACE	Major adverse cardiovascular event
Med-DRA	Medical dictionary for regulatory activities
MI	Myocardial infarction
mITT	modified Intent To Treat
MMP9	Matrix Metallopeptidase 9
MRI	Magnetic Resonance Imaging
MVWA	Mean Vessel Wall Area
NSF	Nephrogenic Systemic Fibrosis
PAV	Percent Atheroma Volume
PCI	Percutaneous Coronary Intervention
PET-CT	Positron Emission Tomography–Computed Tomography
PK	Pharmacokinetic
PL	Phospholipid
PON-1	Serum paraoxonase/arylesterase 1
RBC	Red Blood Cells
RLT	Reverse Lipid Transport
RR	Respiratory Rate
SAE	Serious Adverse Effect
SAP	Statistical Analysis Plan
SBP	Systolic Blood Pressure
SGPT (ALT)	Serum glutamic-pyruvic transaminase/Alanine aminotransferase
SGOT (AST)	Serum glutamic-oxaloacetic transaminase/Aspartate amino transferase
sMCP1	Soluble monocyte chemoattractant protein 1
SUSAR	Suspected Unexpected Serious Adverse Reaction
TAV	Total Atheroma Volume
TBR	Target to Background Ratio
TEAE	Treatment Emergent Adverse Events
TNF $\alpha$	Tumor Necrosis Factor $\alpha$
3T-MRI	3T- Magnetic Resonance Imaging
UAP	Unstable Angina Pectoris
UC	Unesterified cholesterol
ULN	Upper Limit of Normal
VCAM-1	Vascular cell adhesion protein 1
WBC	White Blood Cell

## 3 BACKGROUND

### 3.1 Background on disease familial primary hypolipoproteinemia (FPHA)

ATP binding cassette transporter A1 (ABCA1) and Apolipoprotein (ApoA-1) deficiencies are underlying causes of familial primary hypoalphalipoproteinemia (FPHA). FPHA is caused by genetic defect in one or more of the genes responsible for high-density lipoprotein (HDL) synthesis/maturation, such as ABCA1 and ApoA-1, and is associated with a very low number of HDL-particles, also reflected in a very low plasma concentration of ApoA-1. The disease is also generally associated with a positive family history of low HDL-cholesterol (HDL-C) or premature cardiovascular disease.

The underlying aetiology for all clinical phenotypes of ABCA1 and ApoA-1 deficiencies is the imbalance in cholesterol metabolism. The major carriers for cholesterol in the blood are lipoproteins, including the low-density lipoprotein (or LDL) particles, and the HDL particles. In a healthy human body, there is a balance between the delivery and removal of cholesterol. The LDL particles deliver cholesterol to organs, where it can be used to produce hormones, maintain healthy cells, and be transformed into natural products that assist in the digestion of lipids. The HDL particles remove cholesterol from arteries and tissues to transport it back to the liver for storage, recycling, and elimination through a pathway called “reverse lipid transport (RLT)”.

Mutations in the key HDL gene products, like ABCA1, ApoA-1 and lecithin:cholesterol acyltransferase (LCAT), result in low circulating levels of HDL particles in these patients and, as such, an absent or deficient RLT capacity which is insufficient to prevent the accumulation of cholesterol in the peripheral tissues and results in the development of premature cardiovascular disease.

Current management of patients with FPHA is very limited and is focused on diet control and aggressive LDL-cholesterol (LDL-C)-directed pharmacotherapy that has proven useful adjuncts for managing overall cardiovascular risk. There is no treatment currently available, which can directly restore normal HDL levels/functioning.

Epidemiological studies have consistently shown that decreased HDL-C levels (hypoalphalipoproteinemia) are strongly associated with an increased risk of developing Coronary Arterial Disease (CAD) (1, 2).

#### Mutations in ATP-binding cassette transporter 1 (ABCA1)

In humans, homozygous mutations in the ABCA1 gene leading to defective or non-functional ABCA1 receptors result in Tangier disease, characterized by profoundly decreased HDL-C, ApoA-1 and ApoA-II levels, reduced total and LDL-C and ApoB, and elevated plasma triglyceride levels. With ABCA1 deficiency, ApoA-1 is rapidly cleared before it is able to acquire cholesterol. The cholesterol storage disorder that occurs with ABCA1 mutations might thus possibly be more a consequence of HDL deficiency than a direct consequence of dysfunctional ABCA1 (8).

Homozygous (Tangier disease) patients develop peripheral neuropathy and premature CHD, caused by cholesteryl ester (CE) deposition in a variety of cell types, although the CHD risk differs from one kindred to another, probably because of the reported genetic heterogeneity of the disease (2). Even in heterozygote ABCA1 deficiency patients, radiolabeled HDL was more rapidly catabolized than in healthy controls. Therefore, the metabolic basis of Tangier disease is a rapid catabolism of ApoA-1 and HDL, rather than a defect in their biosynthesis (9). This condition results in an accumulation of CE in many tissues throughout the body, and fibroblasts are characterized by defective efflux capacity. The deposition of CE in the reticuloendothelial organs results in orange-coloured tonsils.

The overall data emerging from studies evaluating patients with ABCA1 mutations are indicative of a link with the development of atherosclerosis and increased vascular disease risk (10, 11).

### **3.2 Atherosclerosis in FPHA**

Atherosclerosis is thought to develop following an imbalance in which there is too much cholesterol delivery by LDL particles relative to the amount of removal by HDL particles.

In animal studies, increasing HDL-C in transgenic mice and rabbits by overexpressing ApoA-1, a major protein in HDL-C, was associated with protection against diet-induced atherosclerosis (12-14).

In humans, FPHA has been reported as highly correlated with higher incidence of premature CAD (15, 16) and tissue cholesterol efflux was decreased in patients with FPHA which co-incided with accelerated and premature atherosclerosis (17).

### **3.3 Investigational Product**

Cerenis Therapeutics has developed CER-001, a negatively charged lipoprotein complex mimicking natural, nascent discoidal pre-HDL, consisting of a combination of two naturally occurring phospholipids and recombinant human ApoA-1. The ApoA-1 protein component is expressed in mammalian CHO cells and purified by a three-step column chromatography process. This purified protein is also referred to as CT70246. The phospholipid component consists of egg sphingomyelin (Sph), and 1, 2-dihexadecanoyl-sn-glycero-3-phospho-(1'-rac-glycerol) (Dipalmitoylphosphatidyl-glycerol; DPPG) in a 97:3 weight ratio. The ratio of protein to total phospholipids in the CER-001 complex is 1:2.7 weight/weight (w/w). The drug product, CER-001 Sterile Solution for Infusion, is a solution of the CER-001 complexes in phosphate buffered sucrose/mannitol solution (10 mM phosphate buffer, 4.0% sucrose, 2.0% mannitol, pH 8.0). The concentration of CER-001 complexes in the formulation is expressed as the concentration of the ApoA-1 protein component of the complex. CER-001 is intended for the treatment of complications due to atherosclerotic diseases.

#### **3.3.1 Non-Clinical Findings for CER-001**

CER-001, a recombinant human ApoA-1/phospholipid complex, was well-tolerated at the dose of 100 mg/kg in rats and monkeys given intravenously (IV), every second day for 4 weeks. A dose of 20 mg/kg, in both species, was considered a dose with no adverse effects in the 4-week dosing studies. CER-001 caused dose-dependent increase in total and free cholesterol, an expected pharmacodynamic effect, as a result of cholesterol mobilization, in both species. CER-001 also caused moderate-to-marked, but transient, increases in liver transaminases, ALT and AST, alkaline phosphatase, total bilirubin and triglycerides at higher doses of 100 mg/kg and above. These changes were generally reversible within 24 to 48 hours post-dose.

Pathological changes in rats included decreased red blood cell indices (evidence of anemia associated with reticulocytosis) consistent with regenerative anemia, dose-related mild-to-moderate hemopoiesis in spleen at 50 mg/kg and above and cholangitis or pericholangitis in liver at 100 mg/kg. These changes were considered secondary to increased cholesterol mobilization and reversible during the treatment-free period.

Liver, spleen and bone marrow were considered target organs of toxicity effect of CER-001. Liver enzyme and renal parameter changes noted in single dose study in rat and rising dose study in monkey at doses 100 mg/kg and above were considered transient and secondary to exaggerated pharmacological effects. These changes were completely reversible within a short treatment-free period.

CER-001 did not cause any treatment-related effects on neurobehavioral parameters and respiratory safety parameters in rats; cardiovascular and respiratory safety parameters evaluated in monkeys implanted with telemetry device at doses up to 100 mg/kg, except but small statistically significant increase in heart rate at 100 mg/kg.

CER-001 did not induce any antibodies against human ApoA-1 in rats after alternate day dosing of CER-001 over a 4 week period. In monkeys, antibodies against human ApoA-1 were detected after alternate day dosing of CER-001 over a 4 week period as well as during the subsequent treatment free period. Further characterization of these antibodies in primates is still being conducted.

### **3.3.2 Clinical Findings for CER-001**

A Phase I single dose tolerance study has been completed in 32 patients. Single doses of 0.25, 0.75, 2.0, 5.0, 10.0, 15.0, 30.0 and 45.0 mg/kg of CER-001 were administered to 32 healthy dyslipidemic volunteers in a randomized, double-blind, placebo-controlled, cross-over, single rising dose safety and tolerance study. CER-001 was well-tolerated in all patients, with an adverse event profile similar to that observed with placebo. CER-001 did not appear to affect clinical chemistry or hematology safety parameters differently than placebo. No adverse effects of CER-001 on ECGs, vital signs, or physical findings were observed. No antibodies against ApoA-1 developed following single doses. All related data can be found in the fifth version of the Investigational Brochure (7).

One Phase II pilot study called EXPRESS, a small 12-patients study in Heterozygous Familial Hypercholesterolemia (FH) to assess MRI and IVUS imaging endpoints, has been completed. The patients enrolled in the study were not representative of the typical high plaque burden/high risk heterozygous FH patient with clinically active atherosclerosis; mean baseline percent atheroma volume (PAV) was only 32% and ranged from 18% to 44%. Non-representative sampling along the length of the coronary arteries by the MHI IVUS Core Lab has raised significant methodological concerns which call into question the appropriateness/applicability of the statistical analysis to the IVUS dataset and the validity of any interpretation of the analytical result relative to the vascular biology of the coronary arteries studied. Given the small number of patients who contributed evaluable data due to measurement difficulties (n=9) and the subsequent methodological concerns, no meaningful conclusions could be drawn regarding the effects of CER-001 on atherosclerotic plaque volume in patients with heterozygous FH. The absence of a detectable treatment response precludes the assessment of the association between the change from baseline in plaque burden measurements as assessed by IVUS and by 3T-MRI. Intravenous infusions of CER-001 administered at a weekly dose of 8 mg/kg for six weeks were well tolerated in these patients with heterozygous FH (7).

A second Phase II study called CHI-SQUARE, in patients with Acute Coronary Syndrome has also been completed. It was an ascending dose, placebo-controlled, double-blind, dose-response study that enrolled 507 patients (3:1 ratio active:placebo). The full study report is still in preparation; however, preliminary results indicate that CER-001 did not meet its primary endpoint of a reduction in total atheroma volume (TAV) as measured by IVUS for the 12 mg/kg CER-001 treated patients compared to the placebo patients. Methodological concerns regarding the IVUS analysis, as detected in the EXPRESS study, also pertain to CHI-SQUARE. An independent and blinded analysis of the IVUS images was conducted by a different IVUS core lab (SAHMRI, Adelaide Australia). In this post-hoc but blinded reanalysis, the 3 mg/kg treatment group showed consistent improvement relative to baseline and was numerically superior to placebo in all analysis populations. In the Modified Per Protocol analysis, statistical significance of 3 mg/kg over placebo was achieved for some of the IVUS measurements (7).

[figure not shown]

Figure 1. Change in IVUS parameters by treatment group and analysis population  
(LS Means from ANCOVA modeling with nonparametric testing due to non-normality of data; mITT = modified intent-to-treat, mPP = modified per-protocol population; PPP = per protocol population)

In general, CER-001 and placebo had a similar safety profile. The incidence and type of SAEs were similar for CER-001 and placebo, with the possible exception of infusion reactions (drug hypersensitivity reactions, anaphylaxis, and adverse drug reactions).

A Phase II study in Homozygous Familial Hypercholesterolemia (HoFH) called MODE has also been completed (18). It was an open-label, single arm active treatment study that enrolled 23 patients. The primary efficacy endpoint was the percent change from baseline to follow-up in carotid artery mean vessel wall area (MVWA). CER-001 produced a clinically meaningful and statistically significant decrease, from a mean of 17.23 mm^2 at baseline to 16.75 mm^2 at Month 6 (2.53%; p=0.0124) in the mITT population (n=18: patients with baseline and follow-up 3T-MRI data). Similar results were seen in the secondary efficacy parameters measuring the effect on the carotid artery. CER-001, administered bi-weekly at a dose of 8 mg/kg for up to 12 months, was well tolerated in these patients. There was only one report of a treatment-related SAE, an urticarial reaction which resolved rapidly with treatment (7).

Importantly, a Phase II study in Familial HDL-C Deficiency also referred to FPHA, called SAMBA, has also been completed. It was an open-label, single arm active treatment study that enrolled nine patients with mutation in ApoA1 and/or ABCA1 gene. The primary study objective was to determine whether the pharmacokinetic and pharmacodynamics behavior of CER-001 was the same in patients with genetic defects affecting the reverse lipid transport pathway. Secondary and exploratory efficacy parameters included measurements of carotid and aortic plaque structure by MRI, carotid plaque inflammation by PET-CT, and fecal elimination of sterols and bile acids. Results from the seven patients who had adequate collection of follow-up data have recently been published (17). The encouraging trial data demonstrated that CER-001 regresses carotid artery inflammation and atherosclerosis and increased elimination of cholesterol from the body. No SAEs were reported nor did any patient discontinue therapy due to an AE. Blood chemistry and hematology findings were unremarkable for this patient population (7).

Recently, the LOCATION study showed that CER-001 is able to target the atherosclerotic carotid plaques in patients with advanced carotid stenosis (*manuscript under preparation*).

### **3.3.3 Description and Mechanism of Action of CER-001**

CER-001 is a complex consisting of recombinant human ApoA-1 and a proprietary combination of charged phospholipids. It is designed to mimic the action of natural nascent, discoidal pre- $\beta$ HDL particles. When injected intravenously, CER-001 is likely to have properties that are similar to newly synthesized endogenous HDL, which is very effective in mobilizing cholesterol from peripheral tissues. More detailed information on CER-001 is provided in the Investigators' Brochure (IB), 5th version, March 2015 (7).

### **3.4 Study rationale**

The encouraging efficacy results seen to date from the CHI SQUARE (ACS), MODE (FH), LOCATION (carotid stenosis) and most importantly SAMBA (FPHA) studies indicate a potential for CER-001 to bring substantial benefit to patients with FPHA. Despite the efforts made on diet control and aggressive LDL-cholesterol (LDL-C)-directed pharmacotherapy, FPHA patients are remaining at high risk for developing cardiovascular event and there is no treatment currently available, which can directly restore functional HDL. Therefore CER-001 represents a potential treatment for those patients and warrant further clinical studies.

This phase III study will confirm whether or not administration of CER-001 will benefit patients with FPHA.

## **4 TRIAL OBJECTIVES**

### **4.1 Primary Objectives**

The primary objectives of the study are:

- To evaluate the effect of 24 week treatment with CER-001 on carotid Mean Vessel Wall Area (MVWA) as compared to placebo using 3T magnetic resonance imaging (3T-MRI);
- To evaluate the safety and tolerability of CER-001 administered for 24 weeks.

### **4.2 Secondary Objectives**

The secondary objectives of the study are:

- To evaluate the effect of 8 week and 48 week treatment with CER-001 on MVWA as compared to placebo using 3T-MRI;
- To evaluate the effect of 8 week, 24 week and 48 week treatment with CER-001 on femoral artery as compared to placebo using 3T-MRI;
- To evaluate the effect of 24 week treatment with CER-001 in the target (plaque) to background (blood) ratio (TBR) from an index vessel (either right carotid or left carotid) based on the standardized FDG uptake measured with PET/CT.
- To evaluate safety and tolerability of 48 week treatment with CER-001.

### **4.3 Exploratory Objectives**

The exploratory objectives of the study include:

- Evaluate the effect of treatment with CER-001 with respect to other efficacy measurements including carotid artery and carotid normalized wall index using 3T-MRI;
- Evaluate the effect of treatment with CER-001 with respect to potential surrogate markers on vessel wall biology including laboratory variables;
- Evaluate the effect of treatment with CER-001 with respect to inflammation;
- Evaluate plasma-mediated cellular Cholesterol efflux capacity;
- ApoA-1 levels (pharmacokinetic parameters);
- Cholesterols, triglycerides, lipids, apolipoprotein and lipoprotein levels (pharmacodynamics parameters).

### **4.4 Other Objectives**

Other objectives of the study include:

- To evaluate safety and tolerability of 72 week treatment with CER-001.
- To evaluate the effect of 72 week treatment with CER-001 on MVWA using 3T-MRI;
- To evaluate the effect of 72 week treatment with CER-001 on femoral artery using 3T-MRI;

## 5 RISK BENEFIT STATEMENT

All patients enrolled in this study will have four 3T-MRI measurements during a time period of 48 weeks. 3T-MRI is a non-invasive imaging technique that does not involve exposure to ionizing radiation. The magnetic field itself is not harmful; however, imbedded metallic fragments such as shrapnel or implanted medical devices that contain metal such as pacemakers may malfunction or cause problems during an MRI exam.

Patients in this study will have two FDG-PET scans during the study, the first one will be performed at baseline and the second and last assessment will be done at week 24. FDG-PET is routinely used in clinical practice. The total radiation exposure in the study corresponding to the two FDG-PET CT scans is 9.4 milli-Sievert. Labelled glucose, F-deoxyglucose, has no known side effects. No adverse effects are expected.

Two thirds of the patients randomized in the trial will receive twenty-nine infusions of CER-001 (8mg/kg) and one third will receive twenty-nine infusion of placebo. More than 400 patients have been exposed to CER-001 in previous clinical trials including 122 patients exposed to 12 mg/kg CER-001 in phase II study. Overall CER-001 has been well tolerated. The incidence and type of SAEs were similar for CER-001 and placebo, with the possible exception of infusion reactions which occurred more frequently with CER-001 and may occur more frequently at higher doses. These reactions were reversible in all cases and either resolved spontaneously or after management with antihistamines, steroids and/or IV fluids. A phase II study (CARAT) aiming to enroll 292 patients for evaluating the potential benefit of CER-001 in ACS patients is currently ongoing.

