**Figure 1. Schematic study design.**

### 6.1.1 Study periods

The study duration can be up to 68 to 92 weeks in total:

- Screening period: up to 16 weeks (+/- 7 days)
- Treatment period: the overall treatment period is 48 weeks (+/- 7 days) including an induction treatment phase of 8 weeks, followed by a 16 week maintenance treatment phase and a 24 week extension treatment phase.
- Safety follow-up period: 4 weeks (+/- 7 days) after the end of treatment OR
- Safety extension follow-up: 24 weeks (+/- 7 days) AND Safety follow-up period: 4 weeks (+/- 7 days) after the end of treatment

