## **8.2 Procedures for Enrollment of Eligible Patients and Assessment at Visit 2**

Once a patient has fulfilled all inclusion and exclusion criteria, he/she will be randomized at visit 2 to receive CER-001 or placebo using an interactive voice response system (IVRS/IWRS). The investigator/designee will contact the IVRS/IWRS to randomize a patient for this study and will be given a patient number and a randomization number. The investigator or designee will use the eCRF with the assigned patient number and the IVRS/IWRS will automatically download the treatment allocation and randomization number as well as the patient number for the patient into the eCRF.

The following assessments will be performed at visit 2 (V2):

- Physical exam (See *Section 8.8.1*)
- Blood Pressure and Heart Rate
- Measurement of weight and vital signs (See *Section 8.8.2*)
- ECG (See *Section 8.8.3*)
- Blood samples for
  - Hematology and coagulation (See *Section 8.8.4*)
  - Serum chemistry (See *Section 8.8.4*)
  - Fasting lipid profile (See *Section 8.9*)
  - Markers of inflammation, oxidation, lipid metabolism and CV risk (See *Appendix A*)
  - Fasting blood glucose and HBA1c
  - Protein biomarker assessment
- Urinalysis (See *Section 8.8.4*)
- Pregnancy test
- Previous and concomitant medication
- Adverse events
- Creatinine and/or BUN testing to determine GFR

Patient must have fasted (ie not to take any food or liquids other than water) for 8 hours prior to blood sampling.

The first 3T-MRI and the first FDG-PET/CT scan assessing the carotid and femoral artery will be optimally performed at this visit prior to the first infusion.

After all assessments have been performed the patient will be administered the first infusion as described in Section 9.6.

He/she will stay for an additional hour after the infusion to ensure completion of the overall examination. A blood sample will be drawn two hours after initiation of the infusion to assess the pharmacokinetics of the study drug.

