## 8.6 Specific Imaging Assessments

### 8.6.1 Assessment of Vascular Structure of the Carotid and Femoral with 3T-MRI

Patients will have 3T-MRI imaging performed at Baseline, Week 8, Week 24, Week 48 and Week 72 (optional) for carotid and femoral Mean Vessel Wall Area (MVWA) and carotid normalized wall index (NVWI) measurements.

The baseline 3T-MRI can be done anytime during the screening period, before the randomization provided all other selection criteria are satisfied.

All images will be collected for their review by an imaging expert, with a window of +/- 7 days around the strict date.

The detailed procedure for performing and collecting of 3T-MRI images will be outlined in the Imaging Manual.

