#### **8.6.2 Assessment of target (plaque) background (blood) ratio with PET/CT**

Patients will have two PET/CT scans with labelled glucose  $^{18}\text{F}$ -deoxyglucose at Baseline and Week 24 only at the sites appropriately equipped.

The baseline PET/CT scan can be done anytime during the screening period, before the randomization.

All images will be collected for their review by an expert, with a window of +/- 7 days around the strict date.

The detailed procedure for performing and collecting PET/CT scans will be outlined in the Imaging Manual.

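### Section 8.6.2 lets the baseline PET/CT be done in screening before eligibility is settled, while section 8.6.1 does not allow this for the radiation-free MRI; the two rules should be reconciled

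*Protocol*

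**What the plan says.** Four parts of the protocol bear on the baseline scans.

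- Section 5 (risk benefit statement) says "3T-MRI is a non-invasive imaging technique that does not involve exposure to ionizing radiation". For FDG-PET it says "the first one will be performed at baseline and the second and last assessment will be done at week 24", and it gives 9.4 mSv as the total for the two PET/CT scans.
- Section 8.6.1, on MRI: "The baseline 3T-MRI can be done anytime during the screening period, before the randomization provided all other selection criteria are satisfied".
- Section 8.6.2, on PET/CT: "The baseline PET/CT scan can be done anytime during the screening period, before the randomization". No eligibility condition follows. The section limits PET/CT to suitably equipped sites, gives a window of 7 days either side of the due date, and leaves procedural detail to the Imaging Manual.
- Section 8.2 says that both first scans "will be optimally performed at this visit prior to the first infusion". The visit meant is Visit 2, when a patient who has met all criteria is randomised.

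Section 6.1.1 allows a screening period of up to 16 weeks. The SAP uses the baseline TBR value but has no rule on when the scan may be taken.

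**The concern.** The two imaging sections are parallel, yet the safeguard is attached to the scan without radiation and is absent from the scan for which section 5 states a dose. The protocol gives no reason for the difference.

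Under 8.6.2 as written, a site may perform the PET/CT while results that decide eligibility are outstanding. If one of them then excludes the patient, that person has been exposed to radiation and can contribute nothing to the TBR endpoint. This is a participant-protection point about a permissive rule. It does not bear on the validity of the primary analysis.

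**Working it through.** **1. The two rules side by side.**

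- MRI (8.6.1): during screening; before randomisation; all other selection criteria already met.
- PET/CT (8.6.2): during screening; before randomisation.

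The first two elements match. The third appears only for MRI.

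**2. Radiation.** Section 5 gives none for MRI and 9.4 mSv for the two PET/CT scans together. The total cannot be reproduced, because the documents give neither a per-scan dose nor an injected activity. If the two scans are equal, one baseline scan is 9.4 / 2 = 4.7 mSv. If they are unequal, the baseline scan is still below the 9.4 mSv total.

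**3. What can be pending when the scan is done.** Section 8.1 collects these samples at Visit 1, and each feeds a criterion in section 7:

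- DNA for the ABCA1 and ApoA-1 genotype (inclusion 5);
- ApoA-1 and HDL-cholesterol (inclusions 8 and 9);
- triglycerides, liver tests, haemoglobin, HbA1c and creatine kinase (exclusions 4, 5, 7, 15 and 16);
- serum pregnancy test (exclusion 10).

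Note 10 to Appendix A describes DNA sampling for patients who would meet all other criteria but have no confirmed mutation. For them the genetic result may be among the last to arrive. Between sampling and result, 8.6.1 does not allow the MRI and 8.6.2 does allow the PET/CT.

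**4. Whether another rule closes the gap.**

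- Section 8.2 states a preference for Visit 2. The same sentence covers both scans, and 8.6.1 still adds its own condition for the MRI.
- Section 8.1 invites only eligible patients to Visit 2. It does not say that no PET/CT may precede that visit.
- The 7-day window (8.6.2 and note 13 to Appendix A) is hard to square with permission to scan at any point in a screening period of up to 16 weeks, so its application to baseline is ambiguous. Even if it applies, it limits the date and does not require eligibility to be settled. The MRI has the same window and the condition as well.

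No provision in the documents forbids a PET/CT before eligibility is confirmed.

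**5. Effect of adding the condition.** A patient with another criterion still open, or already failed, would not be scanned: 0 mSv in place of about 4.7 mSv. A residual remains where a criterion can fail late. Exclusion 14, for example, applies to blood pressure at any visit before randomisation.

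**The case against.** The strongest reply is that the described workflow already puts the scan after eligibility. The Visit 1 list in section 8.1 does not include PET/CT, patients are called to Visit 2 only once eligible, and section 8.2 makes Visit 2 the preferred time. A reader might infer from 8.6.2 that patients who fail screening will be irradiated for nothing. The documents do not support that: they permit an early scan but do not direct one. This part of the reply stands. It does not remove the permission, which 8.6.2 gives in terms.

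A reader might also want a head count. With an assumed screen-failure fraction f, randomising 30 patients means screening 30 / (1 - f). At f = 0.1 that is 33.3, so about 3 failures; at f = 0.3 it is 42.9, so about 13; at f = 0.5 it is 60, so 30. These are counts of failures, and they equal exposures only if every failing patient is scanned first. The documents give no failure rate and no number of equipped sites. Section 6.5 chooses sites by availability of identified patients, and note 10 to Appendix A implies that some arrive with a confirmed mutation, so genotype failures may be few. The true number could be close to zero.

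Two further inferences also fail.

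- That the ethics assessment overlooked this exposure. No such assessment is among the documents, section 14.1 sends the whole protocol to the committee, and one scan is less than the disclosed total.
- That the missing clause weakens the TBR baseline. An early scan is further from the first infusion, but the same holds for the MRI under its existing clause. An eligibility condition sets no limit on the interval from scan to infusion.

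**Conclusion.** The inconsistency between 8.6.1 and 8.6.2 is real and is in the current text. As written, a patient at an equipped site can have the baseline PET/CT while genotype, laboratory or pregnancy results are pending and then prove ineligible. The individual exposure would be about 4.7 mSv, assuming two equal scans. How many patients this would affect cannot be estimated from the documents, and it may be few.

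The sentence in section 5 on scan timing is not itself in error; the conflict lies between the two imaging sections. The point is modest: it touches neither the primary endpoint nor alpha, power or sample size. It merits a change because the exposure is avoidable, no reason is given for allowing it, and the protocol already contains the needed clause.

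**What to change.** Reconcile 8.6.2 with 8.6.1 by giving the baseline PET/CT the condition already used for the MRI, so that it may be done in screening "before the randomization provided all other selection criteria are satisfied". State that the genetic result is one of those criteria.

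The cost is one clause and slightly tighter scheduling of the PET/CT towards the end of screening. It will not bring exposure of non-randomised patients exactly to zero, because some criteria can still fail up to randomisation.
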